2.3. Benefit/Risk Assessment

The key aim of this study is to examine the efficacy and safety of currently recommended and prescribed inhalation therapies to elderly, frail and multimorbid COPD patients with a recent hospitalization due to AECOPD. The study involves a group of patients who have never before been selected for a clinical trial and who represent the 5th most common cause of hospitalization and the 3rd most common cause of death in Italy.

The main objective of this study is to determine whether a long-term inhalation treatment including LABD(s) and ICS, that is currently recommended and shown to reduce symptoms and exacerbations, may also reduce re-hospitalizations and/or death in elderly, frail and multimorbid COPD patients with a recent hospitalization due to AECOPD.

Despite attempts to define the risk of re-hospitalization and death in this population, we could not go beyond an estimated re-hospitalization rate of 20% at 1 month in severe AECOPD (Shah et al 2016), and a re-hospitalization/death rate of 30% at 1 year (Tokgoz et al 2016). However, these estimates were obtained from retrospective studies reported in the literature (Shah et al 2016, Tokgoz et al 2016) that included patients with respiratory failure if they required non-invasive as well as invasive ventilation. In addition, as previously mentioned, the characterization of AECOPD in real life is quite inaccurate, not only as to the nature of the exacerbation of respiratory symptoms (Roca et al 2013) but also in confirming the diagnosis of COPD by spirometry.

For all these reasons, we estimated that by selecting patients with a diagnosis of COPD confirmed by spirometry, even if elderly, frail and with comorbidities, particularly the main chronic heart diseases (CHF, IHD, AF); excluding patients with respiratory failure requiring invasive mechanical ventilation, up to 20% of whom are expected to be re-hospitalized within the first month after a hospitalized AECOPD; and optimizing diagnosis and treatment at the beginning of the study, the rate of re-hospitalization or death will decrease to a maximum of 15% in patients treated with usual care plus LABD(s) but no ICS, whereas we expect that this number will decrease to 9% (40% reduction) by treating them with LABD(s)+ICS.

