3.3 Sample size justification

The sample size calculation is based on the superiority criteria of the LABD+ICS group versus LABD alone group in terms of re-hospitalization and/or death. With 464 patients in each group, the percentage of patients experiencing the composite event (re-hospitalization and/or death) is expected to be 9% in the LABD+ICS group and 15% in the LABD alone group. A log-rank test (two-sided 5% significance level) will have 80% power to detect a difference between treatment groups in terms of time to first re-hospitalization and/or death (primary efficacy endpoint). Adjusting for an expected 10% dropout rate, a total of 516 patients per group will need to be randomized.

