7.2 Analysis of secondary efficacy endpoints

Definitions and data conventions

Number of re-hospitalizations and death

The number of re-hospitalizations and deaths will be calculated per-subject as the sum of the number of hospitalizations as recorded in the ‘COPD Exacerbation Form’ and the deaths (all cause).

Number of moderate/severe COPD exacerbations

The number of moderate/severe COPD exacerbations will be calculated per-subject as the sum of the number of COPD exacerbations recorded as “Moderate” or “Severe” in the ‘COPD Exacerbation Form’.

Number of pneumonia events

The number of pneumonia events will be calculated per-subject as the sum of adverse events classified with the following System Organ Classes/Preferred Terms:

System Organ Class	Preferred Term
Respiratory, thoracic and mediastinal disorders	
 • Pneumonia NOS • Acute pneumonia • Lung infection • Multilobar pneumonia • Bronchopneumonia • Pneumonia lobar • Pneumonia, organism unspecified • Bronchopneumonia NOS • Acute bronchopneumonia • Community acquired pneumonia • Lobar pneumonia NOS • Ventilator associated pneumonia • Healthcare associated pneumonia • Pneumonia recurrent • Bronchopulmonary infection

Forms			
Title	Statistical Analysis Plan Template		
Code	Version	Effective Date	Page
FRM_ST03_032	02	02 Oct 2017	20 of 26

	
 Pulmonary suppuration Lung infection NOS Pleuropneumonia Bronchopneumonia, organism unspecified Bilateral bronchopneumonia Infectious pneumonitis Nosocomial pneumonia Bronchial pneumonia Bilateral pneumonia Hospital acquired pneumonia Right middle lobe pneumonia Lobar pneumonia
--	---

Number of acute cardiac events

The number of acute cardiac events will be calculated per-subject as the sum of adverse events classified with the following System Organ Classes/Preferred Terms:

System Organ Class	Preferred Term
Cardiac disorders	
 Heart failures -Coronary artery disorders Cardiac arrhythmias Embolic stroke Haemorrhagic stroke Thrombotic stroke

Time on study

Time on study (years) will be calculated using the following formula:

Time on study (years) = (Date of patient completion or withdrawal - Date of randomization +1)/365.25.

Log-time on study (years)

The log-time on study in years will be calculated using the following formula:

$$\text{Log-time on study} = \ln(\text{time on study})$$

Statistical analysis

Analysis will be performed on the ITT population.

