Number of re-hospitalizations and deaths

The number of re-hospitalizations and deaths of all cause (1, 2, 3, 4, >4) will be summarised by using frequency distributions and percentages.

Comparison between treatments will be performed using a Poisson regression model. The model will include the number of events as dependent variable, treatment group and center as qualitative independent variables and age as quantitative independent variable. Log-time on study (in years)

Forms			
Title	Statistical Analysis Plan Template		
Code	Version	Effective Date	Page
FRM_ST03_032	02	02 Oct 2017	21 of 26

will be used as an offset. The overdispersion parameter based on the deviance will be considered in order to account for between-patient variability in the event rate and standard errors will be estimated allowing for extra-Poisson variation.

The number of patients and the number of patients considered in the model will be provided by treatment. P-values of the independent variables based on Wald chi-square test will also be presented.

The adjusted mean rates per patient per year in each treatment group and their 95% CIs will be presented, and the adjusted rate ratio between treatments will be provided with the associated 95% Wald CI and p-value.

The following SAS® code will be used to estimate the Poisson regression model:

```
proc genmod data = dataset;
class TMT CENTER;
model VAR = TMT CENTER AGE / offset=log_time dist=poisson link=log dscale wald type3;
lsmeans TMT / exp cl;
lsestimate 'LABD vs LABD + ICS' TMT 1 -1 / exp cl;
run;quit;
```

where VAR represents the number of re-hospitalizations and deaths, TMT the treatment group, CENTER the center, AGE the age and log_time the logarithm of the time on study in years.

The variable tmt will be ordered in SAS in the following order:

- 1 = LABD;
- 2 = LABD + ICS.

Number of moderate/severe COPD exacerbations

The same analyses described for the number of re-hospitalizations and deaths will be performed for the number of moderate/severe COPD exacerbations (1, 2, 3, 4, >4).

Number of pneumonia events

The same analyses described for the number of re-hospitalizations and deaths will be performed for the number of pneumonia events (1, 2, 3, 4, >4).

Number of acute cardiac events

The same analyses described for the number of re-hospitalizations and deaths will be performed for the number of acute cardiac events (1, 2, 3, 4, >4).

Number of deaths

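### Deviance scaling (`dscale`) of the Poisson models shrinks standard errors for rare counts: at the design's event rate, type I error is about 13% to 19%, not 5%

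*SAP*

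**What the plan says.** SAP 7.2 analyses the number of re-hospitalisations and deaths by Poisson regression on treatment, centre and age, with log time on study as offset. On variability it says "The overdispersion parameter based on the deviance will be considered in order to account for between-patient variability in the event rate", and that "standard errors will be estimated allowing for extra-Poisson variation". The code is explicit: "model VAR = TMT CENTER AGE / offset=log_time dist=poisson link=log dscale wald type3". The rate ratio is reported with a Wald CI and p-value. Protocol 9.4.6 also bases the dispersion parameter on the deviance.

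The count itself is defined so: "The number of re-hospitalizations and deaths will be calculated per-subject as the sum of the number of hospitalizations as recorded in the" COPD Exacerbation Form, plus deaths from any cause. The model is reused for exacerbations, pneumonia and acute cardiac events; for pneumonia, "The same analyses described for the number of re-hospitalizations and deaths will be performed for the number of pneumonia events". Protocol 9.4.8 also repeats the re-hospitalisation/death count analysis in the LAMA+LABA with or without ICS subgroup; SAP 7.2 does not carry that repeat over.

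Neither document sets a lower bound of 1 on the scale, uses a Pearson scale, or says what to do if the estimate falls below 1. SAP 4.8 lists no change on this point. Tests are two-sided at 0.05 (SAP 4.1), and protocol 9.4.5 plans no multiplicity adjustment.

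On event rates, SAP 3.3 says the percentage with the composite event "is expected to be 9% in the LABD+ICS group and 15% in the LABD alone group". Protocol 2.3 cites up to 20% re-hospitalised in one month "and a re-hospitalization/death rate of 30% at 1 year", then argues that with this trial's selection and optimised care "the rate of re-hospitalization or death will decrease to a maximum of 15" percent without ICS.

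**The concern.** Deviance/df is a usable dispersion estimate only when expected counts per patient are not small. When most patients have zero events, the deviance is far below its degrees of freedom even if the Poisson model is exactly right. `dscale` reads this as underdispersion and shrinks the standard errors, the opposite of the purpose the SAP states for it.

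At stake are the p-values and intervals of four secondary counts. Pneumonia matters most, because whether ICS raises its risk is a named secondary objective. A chance difference in a sparse count, in either direction, could be declared significant at 0.05 far more often than intended.

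**Working it through.** **Inputs.** 9% and 15% with an event, 464 evaluable and 516 randomised per arm, 10% dropout (SAP 3.3); 39 centres (protocol synopsis); two-sided 0.05 (SAP 4.1); 12 months of treatment plus 3 of follow-up (SAP 3.1). Assumed, because the documents are silent: blocks of 4, centre sizes (equal, or unequal with gamma(1.5) weights), and overdispersion k, with variance μ + kμ², taken as 0 (Poisson) or 1.

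**The plan's own figure.** HR = ln(0.91)/ln(0.85) = 0.580. Freedman's formula gives (1.960 + 0.842)² × (1.580/0.420)² = 111.3 events; 111.3/(0.09 + 0.15) = 463.7, so 464 per arm; 464/0.9 gives 516. Both are reproduced, so 9% and 15% are the rates the trial was sized on.

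**Rates.** −ln(0.91) = 0.0943 and −ln(0.85) = 0.1625, mean 0.1284 per patient-year. The cited 30% gives −ln(0.70) = 0.357.

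**Analytic check.** For a Poisson count with mean μ the expected unit deviance is φ = 2 Σ p(y) y ln(y/μ), summed over y ≥ 1. At μ = 0.1284:

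- y = 1: 0.1129 × 2.053 = 0.2318
- y = 2: 0.00725 × 5.49 = 0.0398
- y = 3: 0.00031 × 9.45 = 0.0029
- y ≥ 4: 0.0001

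The sum is 0.2746, so φ = 0.549. The actual error is 2[1 − Φ(1.96 √φ)] = 2[1 − Φ(1.452)] = 14.6%. The same formula gives 6.3% at 0.357 (φ = 0.900), 4.9% at 0.50 (φ = 1.007) and 3.6% at 1.0 (φ = 1.147). The shrinkage therefore ends at about 0.5 events per patient.

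**Simulation of the SAP model under the null.** 1,032 patients, 39 centres, centre + age + treatment, 10% dropout, 4,000 trials per setting (Monte Carlo SE about 0.6 percentage points at 16%). Where two figures appear they are equal/unequal centres.

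| Rate per year | Basis | Follow-up | `dscale`, Poisson | `dscale`, k = 1 |
|---|---|---|---|---|
| 0.05 | assumed | 12 months | 32.2% | 35.1% |
| 0.128 | design | 12 months | 16.6/16.1% | 18.5/18.7% |
| 0.128 | design | 15 months | 14.2/13.5% | 16.7/15.0% |
| 0.357 | cited 30% | 12 months | 6.3/7.3% | 9.5/10.1% |
| 0.357 | cited 30% | 15 months | 5.2/5.2% | 8.4/8.4% |
| 0.50 | assumed | 12 months | 5.5% | 8.7% |
| 1.0 | assumed | 12 months | 4.0% | 6.9% |

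At the design rate with Poisson data, mean deviance/df was 0.506 (12 months) and 0.58 (15 months). At 12 months with equal centres the mean `dscale` SE was 0.128 against a true SD of 0.183, a ratio of 0.70.

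**Coverage of the 95% CI under the planned effect** (0.163 against 0.094 per year, equal centres): `dscale` 83.9% (12 months) and 85.9% (15 months) for Poisson data, 81.3% and 84.0% with k = 1; robust SEs 94.6% to 94.7%; Pearson scaling 94.3% to 95.0%.

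**Alternatives under the null.** Robust SEs gave 4.9% to 5.9% across all 22 settings. Pearson scaling gave 5.0% to 6.1% at 0.128 and 4.4% to 6.0% at 0.357, but 9.5% and 11.0% at 0.05. A floor at 1 works for Poisson data but not with real overdispersion: with frailty variance 1 to 3, mean counts of 0.09 to 0.15 and no centre terms, it gave 6.5% to 10.3%.

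SAS was not run. The fitting code matched a standard GLM routine on a test dataset (estimate, SE, deviance/df, Pearson/df and robust SE).

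**The case against.** The strongest objection is that 9% and 15% are proportions of patients with a first event, used to size a log-rank test, and are not rates for the modelled count. That count adds repeat events, which raises it, but takes hospitalisations only from the COPD Exacerbation Form, which may lower it. No document gives the rate or dispersion of any of the four counts. At the cited 30% per year the inflation for Poisson data is slight, and near one event per year `dscale` is mildly conservative. The exacerbation count adds moderate events to the hospitalised ones, so it should be no rarer than the COPD hospitalisation component.

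This stands as a limit on size: 13% to 19% is conditional and not a bound. If no patient had more than one event (928 patients, no centre terms), the error is 10.1% at a common 15% and 18.5% at a common 9%. Repeat events do not rescue the method, however. With strong clustering (assumed 0.2 per year, k = 6) the error was about 22%. At 0.357 per year with k = 1, the kind of variation the scaling is meant to absorb, it is still 8% to 10%.

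It is also fair that a missing floor is only part of the fault, since a floor alone under-corrects overdispersed data. The root cause is using the deviance as the scale for sparse counts. Finally, the success claim rests on the log-rank test, and the secondary p-values are unadjusted and carry no confirmatory claim. That limits the severity but does not make the intervals right.

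**Conclusion.** The point holds. At the rate on which the trial was sized, the planned standard errors are about 30% too small, the nominal 5% test rejects about 13% to 19% of the time, and the 95% interval for re-hospitalisations and deaths covers 81% to 86%. The upper end rests on an assumed k = 1; centre sizes barely alter the range. Confidence is high in the mechanism and lower in the exact percentages.

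Rarer counts fare worse: about 32% to 35% at an assumed 0.05 per year, which would apply to pneumonia or cardiac events only if they are that rare. Frequent, near-Poisson counts are little affected. The primary analysis and the tabulated cardiovascular deaths are untouched. This should be fixed, but it does not threaten the trial's main conclusion.

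**What to change.** In SAP 7.2, replace the deviance-based dispersion sentence with robust (sandwich) standard errors for all four modelled counts. In the code, drop `dscale`, add the patient identifier to the `class` statement, and add `repeated subject=PATIENT;`. Confirm in the validated program that the `lsmeans` and `lsestimate` output uses the empirical standard errors. Align protocol 9.4.6 or list the change in SAP 4.8. If the SAP can no longer be amended, report the robust result beside the planned one and explain it in the clinical study report, as the SAP introduction provides for deviations.

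The smallest edit is `pscale` in place of `dscale`. It is adequate for Poisson or moderately overdispersed data at 0.128 per year and above, but it is too narrow for much rarer counts (9.5% to 11% at 0.05 per year) and drifts to about 8% under the strong clustering described above. A floor at 1 alone is not enough.

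The cost is some wording and one statement, with no change to design, data or sample size. Intervals for sparse counts become wider and correct, so fewer secondary results will be nominally significant. Near one event per year with Poisson data the interval narrows a little (mean SE from 0.068 to about 0.063).

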1. Patients with a primary discharge diagnosis of DRG 087 or DRG 088 but clearly judged by the clinical investigator to be due to other causes, i.e. patients presenting to the hospital with symptoms of AECOPD but due mainly to other conditions (pulmonary embolism, pneumonia, pneumothorax, anemia, acute kidney failure, decompensated heart failure, acute ischemic heart disease, new onset atrial fibrillation, stroke, etc.)
2. Patients who required invasive mechanical ventilation during hospitalization
3. Patients with Asthma as primary and principal diagnosis
4. Patients with severe cardiovascular (CV) disease who in the opinion of the investigator are unlikely to survive the 15 month study period
5. Patients considered unable to comply with the study procedures and follow-up in the opinion of the investigator (eg, evidence of alcohol or drug abuse, psychiatric disorder, physical disability, social or geographical obstacles)
6. Patients in whom spirometry is contraindicated (eg, hemoptysis, detached retina, active tuberculosis, last trimester of pregnancy)
7. Patients with other mechanical or overt causes of respiratory symptoms, particularly dyspnea (such as pneumothorax, chest wall trauma, lung fibrosis, lung cancer, anemia, severe obesity (BMI >40) or cachexia (BMI <18))
8. Patients with any major disease which in the opinion of the investigator would prevent study participation, such as dementia, end-stage disease, cachexia, chronically bedridden patient and life expectancy <15 months.
9. Participation in any other interventional study within the last 3 months or concurrent participation in an observational clinical study.

Number of Participants:

The aim is to randomize 464 participants to each intervention group

Adjusting for an expected 10% dropout rate, a total of 516 patients per group will need to be randomized.

The study will be performed at 39 centers in Italy.

Intervention Groups and Duration:

In this study patients will be randomised to receive one of the following two treatment regimens for up to 12 months:

- 1) Usual and optimized treatment for concomitant cardiovascular (CV) diseases plus inhaled long acting bronchodilator(s) (LABD(s))

2) Usual and optimized treatment for concomitant CV diseases plus inhaled long acting bronchodilator(s) and inhaled glucocorticosteroids (ICS).

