4.5 Pooling of sites

Not foreseen.

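### The adjusted annual event rates in SAP 7.2 break down whenever a centre has no event, because they average 39 unpooled fixed centre effects equally on the log scale

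*SAP*

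**What the plan says.** SAP 7.2 compares the number of re-hospitalizations and deaths between arms with an overdispersed Poisson regression on treatment, centre and age, with log time on study as offset. Besides the rate ratio, it reports a rate for each arm: "The adjusted mean rates per patient per year in each treatment group and their 95% CIs will be presented".

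The code printed there fixes how this is done. Centre is a class variable ("class TMT CENTER") and enters as an ordinary fixed effect ("model VAR = TMT CENTER AGE / offset=log_time dist=poisson link=log dscale wald type3"), with no random statement. The arm rates come from "lsmeans TMT / exp cl", with no option that weights centres by their observed size.

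The same analysis is carried over to exacerbations, pneumonia and acute cardiac events; for pneumonia: "The same analyses described for the number of re-hospitalizations and deaths will be performed for the number of pneumonia events". The Protocol synopsis gives the number of sites: "The study will be performed at 39 centers in Italy". The SAP section headed "4.5 Pooling of sites" plans none. Neither document says what to do with a centre that has no event.

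**The concern.** By default, `lsmeans` gives every level of a class variable the same weight. Here it averages 39 centre coefficients on the log scale and then exponentiates. A fixed centre effect with zero events has no finite maximum-likelihood estimate. The software stops at some large negative number, and that number enters the average with weight 1/39. The adjusted rate is then set partly by a convergence criterion, and its standard error explodes.

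Whether ICS raises the risk of pneumonia is a named secondary objective, and pneumonia is likely to be among the rarer counts. The rates from this code are the only annual rates per arm with a CI that the SAP prespecifies. If the problem is noticed only after the results are seen, any replacement is post hoc in an open-label trial.

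**Working it through.** **Patient numbers (Protocol 9.2, SAP 3.3).** HR = ln(0.91)/ln(0.85) = 0.580. Freedman's formula with two-sided 5% and 80% power gives 111.28 events. 111.28/(0.09 + 0.15) = 463.7, so 464 per group, and 464/0.9 gives 516. The plan's figures reproduce. Totals are 928 and 1,032 patients, i.e. 23.8 or 26.5 per centre if the 39 centres are equal.

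**How often a centre has no event.** P(none in a centre) = exp(-n × rate), and P(at least one such centre) = 1 - (1 - p)^39. With equal centres:

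| Mean rate per year | Patients | Expected zero-event centres | P(at least one) |
|---|---|---|---|
| 0.06 (pneumonia, assumed 0.05/0.07) | 1,032 | 8.0 | 1.00 |
| 0.12 (mean of 9% and 15%) | 1,032 | 1.6 | 0.81 |
| 0.12 | 928 | 2.2 | 0.90 |
| 0.13 (9%/15% taken as about 0.095/0.165 per year) | 1,032 | 1.3 | 0.72 |
| 0.20 | 1,032 | 0.2 | 0.18 |
| 0.25 | 1,032 | 0.05 | 0.05 |

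Unequal centres raise these figures. With an assumed spread of about 3 to 116 patients per centre, 6 to 7 centres have no event at a rate of 0.12. At a rate of 0.30 the chance of at least one is still about 0.80.

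**What zero-event centres do to the rate.** If the software stops at log-rate b, k such centres multiply both arms' rates by exp(k × (b - ln rate)/39). The documents do not give b, so a range of -15 to -30 is used; the fits run for this check stopped at about -22 to -27.

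- Rate 0.12, ln = -2.12. One centre: exp((-15 + 2.12)/39) = 0.72, down to exp((-30 + 2.12)/39) = 0.49. Two centres: 0.52 to 0.24.
- Rate 0.06, ln = -2.81, eight centres: the factor is 0.082 at b = -15, 0.011 at -25 and 0.004 at -30. The reported rate is about 0.005, 0.0006 or 0.0002 instead of 0.06.

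**Simulation.** Poisson fits with 39 equal centres and no centre variation; true rates are LABD/LABD+ICS.

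| Scenario | LSMEANS | Crude | Standardised, same fit |
|---|---|---|---|
| 0.15/0.09, 928 patients | 0.041/0.023 | 0.152/0.090 | 0.154/0.090 |
| 0.165/0.095, 1,032 patients | 0.062/0.035 to 0.083/0.046 over three runs | about 0.17/0.09 | 0.166/0.09 |
| 0.05/0.07, 1,032 patients | 0.0003/0.0004 to 0.0005/0.0008 over three runs | 0.051/0.071 | 0.05/0.07 |

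The runs differ because the medians depend on how many zero-event centres are drawn. With such a centre present, the standard error of the log rate was in the hundreds or thousands, so the 95% CI is in effect 0 to infinity.

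**Without zero-event centres.** The result is a geometric mean over centres. In the simulations it was 0.80 to 0.96 of the crude rate, but it can also lie above it. Take 10 centres of 60 patients at rate 0.2 and 29 centres of 15 at rate 0.4. The geometric mean is exp((10 ln 0.2 + 29 ln 0.4)/39) = 0.335. The patient-weighted rate is (120 + 174)/1,035 = 0.284.

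**Rate ratio.** The centre terms cancel in the difference between arms. Removing the zero-event centres changed the log rate ratio by less than 1e-10.

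**The case against.** The strongest reply is that no between-arm conclusion depends on these numbers. A reader might infer that the pneumonia comparison itself is compromised. It is not: the rate ratio, its CI and its p-value do not pass through the averaging over centres, and the primary log-rank and Cox analyses do not use this code. Absolute burden is also visible elsewhere. SAP 7.2 tabulates the number of events per patient, and SAP 8.1 gives numbers and percentages of patients by preferred term and arm. An adjusted rate of 0.0005 beside about 5% of patients with pneumonia would probably be noticed, and the SAP introduction provides for deviations to be explained in the study report. All of this stands and limits the severity. It does not rescue the stated output, because no other annual rate with a CI is planned.

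A second reply is that the sizes are assumed. The documents give no pneumonia rate, no centre sizes and no between-centre variation. The 9% and 15% are first-event proportions, not recurrent-event rates. The fits were generic Poisson regressions, so the stopping value in SAS may differ. This also stands. A reader might infer that the admission rates are bound to be wrong, but the documents do not support that. Protocol 2.3 cites about 30% re-hospitalization or death at one year from the literature, and at a mean rate of 0.25 or more with equal centres a zero-event centre is unlikely.

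Nor is the adjusted rate always too low. When every centre has events, an equally weighted mean is a conventional quantity that can lie on either side of the patient-weighted rate.

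**Conclusion.** The point holds for the per-arm adjusted rates and their CIs. With any zero-event centre, the printed code returns a rate set partly by the stopping rule and a CI that carries no information. For pneumonia this is near certain at the assumed 0.05 to 0.07 per year. For re-hospitalizations and deaths it is likely (about 70 to 90%) at the plan's own 9%/15% with equal centres, and unlikely at 0.25 per year or more with equal centres; unequal centres raise the chance. Exacerbations and acute cardiac events use the same code, but the documents give no rate from which to size the problem. Because the treatment comparisons and the primary analysis are intact and raw counts are reported, this should be fixed before analysis but does not threaten the trial's conclusions.

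**What to change.** In SAP 7.2, for all four count endpoints, replace the `lsmeans` rates by standardised rates from the same fitted model. Predict each ITT patient's rate over one year under LABD and under LABD+ICS, and average over all ITT patients. Give a CI by a method that stays valid when some centres have no event, for example a bootstrap. State in the text that centres without events remain in the model. Leave the planned model and rate ratio unchanged.

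Making centre a random effect is not an equivalent remedy. It changes the model behind the rate ratio, and its default adjusted rate is still a geometric mean: about exp(-0.5²/2) = 0.88 of the marginal rate if the between-centre log SD is 0.5.

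The cost is a few lines of SAP text and a short macro. No new data are needed.
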